## PROTOCOL SYNOPSIS

Title	COVID-19 Vaccination Status and The Characteristics and Clinical Outcomes of Long COVID-19 Patients in [name] General Hospital
Sponsor	University of Indonesia
Study Rationale	
Long COVID is the persistence or emergence of symptoms for more than four weeks beyond the acute phase of Severe Acute Respiratory Syndrome – Coronavirus-2 (SARS-CoV-2) infection. Various multi-organ complications after COVID-19 infection include respiratory, cardiovascular, gastrointestinal, hepatobiliary, metabolic, and neuropsychiatric disorders. The symptoms and characteristics of Long COVID vary in each country.
 
Vaccination against SARS-CoV-2 has been documented to increase the clinical resolution of Long COVID. However, in Indonesia, current full-dose vaccination coverage has merely reached 15.6% of the national vaccination target. This condition can be predictably associated with a longer duration and higher severity of symptoms in Long COVID patients.
 
This study's point of view is to describe the incidence and the characteristic of long COVID in patients and the impact of COVID-19 vaccination on the clinical outcome of long COVID. In addition, this study is expected to reinforce the recommendation for the COVID-19 vaccine implementation in Indonesia. The result of this study can be applied in clinical practice to ascertain the benefits of SARS-CoV-2 vaccination to improve clinical outcomes and quality of life; and reduce symptoms, duration, and frequency of long COVID.

Study Objectives	
Primary
 
 
• To provide an overview of the symptoms and characteristics of Long COVID patients at [name] General Hospital.
 
• To determine whether vaccination against SARS-CoV-2 could improve clinical outcomes and quality of life of Long COVID patients at [name] General Hospital.
 
 
Secondary
 
 
• To determine whether vaccination against SARS-CoV-2 could increase functional exercise capacity of Long COVID patients.
 
• To determine whether vaccination against SARS-CoV-2 could reduce symptoms, duration, and frequency of Long COVID.
 

Study Design	Prospective cohort study

Subject Population Key criteria for Inclusion and Exclusion:	
Inclusion Criteria
 
 
1. Adult patients, aged <math>\geq 18</math> years old with a history of laboratory-confirmed SARS-CoV-2 infection via a positive molecular (RT-PCR) or antigen (lateral flow assay) test, receiving outpatient/inpatient care from [name] General Hospital, any time prior to enrollment in this study.
 
2. Patients with/without comorbidities.
 
3. Willing to fill-out online Long COVID symptoms follow-up questionnaire.
 
4. Willing and able to comply with the trial protocol, 6 Minutes Walking Test (re-visits and physical testing).
 
 
Exclusion Criteria
 
 
1. Patients with no registered medical record number (MRN) at [name] General Hospital.
 
2. Refusal to participate in the study or to sign the informed consent form.
 
3. Contraindicated to perform the 6 Minutes Walking Test.
 
4. Patients with no access to a smartphone or computer (desktop, laptop, or tablet) to fill out the online screening questionnaire.
 
5. Patients who died during or before enrollment in the study.
 

Number of Subjects	
A total of 250 subjects are divided into 4 groups according to SARS-CoV-2 vaccination status:
 
 
• Never been vaccinated.
 
• Received 1st dose of vaccination.
 
• Received 2nd dose of vaccination.
 
• Received 3rd dose of vaccination.
 

Study Location	[name] General Hospital, Central Jakarta, Jakarta, Indonesia
Study Duration	Each subject's participation will last for 6 months. The estimated duration for the main protocol is approximately 1 year.
Study Phases	
Screening Screening for eligibility and obtaining consent.
 
Study Examination Online questionnaire filling, 6-Minute Walking Test (6MWT)
 
Follow-up Follow-up examination 3 and 6 months after baseline.

Safety Evaluations	
Adverse events will be monitored and collected by the study team from the point of signed consent until the adverse event(s) are resolved and subjects are stabilized. Adverse events will be managed according to the 6MWT guidelines of the American Thoracic Society (ATS).

---

Statistical and Analytic Plan	Statistical analyses will be performed using SPSS version 20. Descriptive statistics will describe the incidence of long COVID in participants and its characteristics, the clinical outcome, and the quality of life. The bivariate analysis will be performed using chi-square or fisher , to find the correlation between COVID-19 vaccination status and the characteristics and clinical outcomes of long COVID patients. The value of the limit of significance is 0.05.
Data and Safety Monitoring Plan	If there were any serious adverse events (SAE), the case will be reported to the ethics committee as soon as possible, less than 24 hours from the first time they were discovered, and actions were carried out as quickly as possible until the series of events ends. SAE was written in detail on the SAE form, including the following; when it was first discovered, the manifestation of the incident, the conditions before the incident, the handling of the event, and the outcome.

---

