## 5.4. Data Collection

Data on age, sex, height, weight, body mass index, income, education, comorbidities, smoking, alcohol consumption, documented SARS-CoV-2 vaccination

status (including the amount, type, and when the vaccine was received), detailed history of laboratory-confirmed SARS-CoV-2 infection, Long COVID symptoms, severity, and duration are collected through online screening questionnaire.

Data on quality of life (QoL) are collected through St George's Respiratory Questionnaire (SGRQ) and Short Form (SF)-36 Health Survey self-assessment questionnaire at baseline, 3 and 6 months after enrollment. SGRQ addresses QoL in the domains of symptoms, activity, and impacts within the last 4 weeks; and the SF-36 Health Survey questionnaire addresses QoL in the domains of vitality, physical functioning, bodily pain, general health perceptions, physical and emotional and social role functioning.

Data on functional exercise capacity is measured using the Six-Minute Walking Test (6MWT) at baseline, 3 and 6 months after enrollment. The 6MWT is performed according to the guidelines of the American Thoracic Society (ATS). During the 6MWT, such data are collected: Blood pressure, oxygen saturation (SpO2), heart rate, dyspnea, and overall fatigue score using the Modified Borg scale before and after the test, and also one-time measurement (total distance walked in 6 minutes, symptoms at the end of exercise).

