## STATISTICAL ANALYSIS PLAN

### 1. Randomization

Subjects who meet all inclusion and exclusion criteria will be allocated into four groups; Never been vaccinated, received 1st dose, received 2nd dose, and received 3rd dose of vaccination. Subject allocation will be carried out through block randomization and known only by the pharmacist, and confidentiality is maintained so that subjects, doctors/nurses, researchers, and data analysers do not know the allocation of each subject.

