##### **3.2.1. Univariate analysis**

The analysis is intended to obtain descriptive data regarding the incidence of long COVID events and the characteristic profile of long COVID patients.

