##### **3.2.2. Bivariate analysis**

This analysis is used to see the relationship between the effect of the COVID-19 vaccine on clinical long COVID and the quality of life of long COVID patients. The level of significance used is 0.05. Variables are statistically significant if p-value <0.05. The independent variables in this study are nominal scale, so the test used in this analysis is the chi-square test or fisher's test (in the group of independent variables with a dichotomous scale of 2x2 if the chi-square does not meet the requirements.

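### Vaccine type is collected but has no stated role in the analysis; if the mix of types differs across the 1-, 2- and 3-dose groups, a difference among them cannot be attributed to dose number

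*Combined protocol and SAP*

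**What the plan says.** The exposure is defined by number of doses. The synopsis (Number of Subjects) says "A total of 250 subjects are divided into 4 groups according to SARS-CoV-2 vaccination status" and lists never vaccinated, first, second and third dose. SAP 1 repeats the grouping: subjects "will be allocated into four groups; Never been vaccinated", followed by the same three dose levels. Vaccine type appears in neither definition, and the eligibility criteria do not restrict it.

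Type is nevertheless recorded. Protocol 5.4 collects documented vaccination "status (including the amount, type, and when the vaccine was received", among other items.

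The analysis has two steps. SAP 3.2.1 is descriptive: "The analysis is intended to obtain descriptive data regarding the incidence of long COVID events" and the profile of long COVID patients. SAP 3.2.2 is bivariate: "The independent variables in this study are nominal scale, so the test used in this analysis is the chi-square test or fisher's test". The synopsis gives the same purpose, "to find the correlation between COVID-19 vaccination status and the characteristics and clinical outcomes of long COVID patients". The text describes no stratified, restricted or multivariable analysis, by type or by anything else.

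**The concern.** Dose number and vaccine type are two parts of one exposure. If third doses, say, tend to be of another type than the first two, the three-dose group differs from the two-dose group in both respects at once, and an unadjusted test of dose group responds to either. SAP 3.2.2 does not list its independent variables, so type might be tested as a further factor. That would not solve the problem, because two separate one-factor tests cannot disentangle two associated factors.

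At stake is the reading of differences among the one-, two- and three-dose groups. The synopsis expects the results to support vaccination recommendations, and a gradient across dose groups could easily be read as the benefit of a further dose when part or all of it reflects type.

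**Working it through.** **1. The plan's own figure.** SAP 2 (analytic study) uses P1 = 0.653, P2 = 0.453, P = 0.553, 1.96 and 0.80.
- 1.96 × √(2 × 0.553 × 0.447) = 1.378
- 0.80 × √(0.653 × 0.347 + 0.453 × 0.547) = 0.551
- n = ((1.378 + 0.551) / 0.20)² = 93.0; 2 × 93 = 186; 186 + 37 = 223

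The stated figures reproduce. They size one comparison of two groups with a minimal difference of 0.20. The point here does not depend on them; they only supply the scale.

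**2. How a type difference becomes a dose difference.** Take two types, A and B, with outcome proportions pA and pB, and no effect of dose number. If a share s of a dose group received B, its expected proportion is pA + s(pB − pA). For two dose groups g and h:

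spurious difference = (pB − pA) × (s_g − s_h)

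Assumed ranges, not in the documents: pB − pA from 0.10 to 0.20, and s_g − s_h from 0.20 to 0.60.
- Smallest: 0.10 × 0.20 = 0.02
- Largest: 0.20 × 0.60 = 0.12, which is 0.12 / 0.20 = 60% of the plan's minimal difference

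**3. Why a separate test of type does not help.** Borrow the plan's two proportions for the types: A = 0.453, B = 0.653. Let B make up 20% of the two-dose group and 80% of an equally large three-dose group.
- Only type matters: two doses 0.453 + 0.20 × 0.20 = 0.493; three doses 0.453 + 0.80 × 0.20 = 0.613. Dose groups differ by 0.12, types by 0.20.
- Only dose matters (0.453 with two doses, 0.653 with three): type A 0.80 × 0.453 + 0.20 × 0.653 = 0.493; type B 0.613. Types differ by 0.12, dose groups by 0.20.

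Both one-factor comparisons show a difference in both situations. Only a comparison of dose groups within type tells them apart.

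**4. Chance of a significant result with no dose effect.** Assume four equal groups (250 / 4 = 62.5, taken as 62; the documents give no group sizes), proportions centred on 0.55, and one pairwise two-sided test at 0.05. For a spurious difference d:

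probability = Φ((d − 1.96·SE0) / SE1) + Φ((−d − 1.96·SE0) / SE1)

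Here SE0 = √(2 × 0.55 × 0.45 / 62) = 0.0894 and SE1 is the unpooled standard error. For d = 0.12, SE1 = √((0.61 × 0.39 + 0.49 × 0.51) / 62) = 0.0887, which gives 0.268.

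| Spurious difference | Chance of p < 0.05 |
|---|---|
| 0.02 | 0.056 |
| 0.04 | 0.073 |
| 0.08 | 0.145 |
| 0.12 | 0.268 |

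**5. What stratifying costs.** With equal groups of 62.5, power for 0.653 versus 0.453 in one pairwise comparison is about 62%. Within a single type, if each group splits evenly in two (about 31 per cell), it is about 35%. A stratified test pools the strata and loses less. With the 20% / 80% shares of step 3, each stratum compares 12.5 with 50 subjects and carries 12.5 × 50 / 62.5 = 10 units of information, 20 in all, against 62.5 × 62.5 / 125 = 31.25 unstratified. That is 20 / 31.25 = 64%, so intervals are about 1 / √0.64 = 1.25 times as wide, if variances are similar. If the types do not overlap between two dose groups, the information is zero and no analysis can separate dose from type.

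**The case against.** The strongest case against is that the plan asks a different question. Every objective in Protocol 2 concerns vaccination, not an additional dose, and the sample size is for two groups. For vaccinated versus never vaccinated, type cannot confound, since the unvaccinated have none; the contrast averages over the vaccines patients received, which suits a recommendation that is not product-specific. This stands, and it confines the point to contrasts among the vaccinated groups. A reader might infer that type undermines the study's main vaccination question as well; the documents do not support that. It does not remove the point, because the plan forms three vaccinated groups by dose count and tests across them.

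Other stronger readings also fail:
- **That the mix of types goes unrecorded.** Protocol 5.4 records it. What is missing is a stated analysis.
- **That the dose groups do differ in type.** No section names a vaccine or gives the mix. A data field for type shows only that more than one was allowed for.
- **That counting doses misclassifies complete courses.** The full-dose wording in the rationale is a national coverage figure; nothing defines completeness by type.

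It is also fair that type is one of several collected but unadjusted factors, alongside age, comorbidities, infection history and timing of vaccination. A prespecified adjusted model that included type would answer most of this point.

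In the other direction, the block randomization in SAP 1 cannot be relied on to balance type. It conflicts with a cohort grouped by vaccination that is already documented.

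Finally, the figure under SAP 3.2 and the flow diagram under SAP 4 were not available to me. The surrounding text describes no adjusted analysis.

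**Conclusion.** The point holds as a limited gap in the analysis plan. Type is collected without a stated use, and unadjusted tests by dose count cannot separate dose number from type among the one-, two- and three-dose groups. Whether this produces bias depends on two things the documents do not give: how the mix differs by dose group, and whether types differ in their relation to outcome.

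The illustrative spurious difference is 0.02 to 0.12, with a chance of a significant pairwise result of about 6% to 27% instead of 5%. That range rests wholly on assumed type effects and shares, equal groups of 62, and a pairwise test the plan does not specify. At the low end the effect is negligible. The high end requires two types to differ by the plan's whole minimal difference. The figures show what is possible, not what is expected.

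**What to change.** In SAP 3.2.2:
1. Tabulate vaccine type by dose group, marking each third dose as the same type as the primary series or a different one. This alone shows whether the issue is live.
2. Keep the overall dose-count comparison. Add, as a supportive analysis, a comparison of the one-, two- and three-dose groups stratified by primary-series type: Cochran-Mantel-Haenszel (generalised form, or pairwise, for three groups), or type as a term in an adjusted model.
3. Show vaccinated versus never vaccinated by type, against the common unvaccinated group, with confidence intervals.
4. Where type and dose cannot be separated, for example if nearly all third doses are of another type, describe differences among dose groups as associations with vaccination history and not as effects of dose number. Stratifying by primary-series type does not rescue that case.

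Two further steps are not advised: a variable for course completeness by type, which the documents give no basis to define, and a rule that accepts a dose effect if its direction holds in the commonest type, which noise would pass about half the time.

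The cost is SAP wording and a few tables from data already collected. The downside is small strata and wide intervals, so the stratified results should be reported as estimates with intervals and not judged by significance.

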## **STUDY PROTOCOL**

### **1. Introduction**

Long COVID is defined by the persistence or emergence of symptoms for more than 4 weeks beyond the acute phase of Severe Acute Respiratory Syndrome-Corona Virus-2 (SARS-CoV-2) infection. As the number of cases increases and various strains of SARS-CoV-2 emerge, so does the number of long COVID cases. Various multi-organ complications after COVID-19 infection include respiratory, cardiovascular, gastrointestinal, hepatobiliary, metabolic, and neuropsychiatric disorders. The symptoms and characteristics of Long COVID vary in each country.

Vaccination against SARS-CoV-2 has been documented to increase the clinical resolution of Long COVID. In Indonesia, current full-dose vaccination coverage had merely reached 15.6% of the national vaccination target. This condition can be predictably associated with a longer duration and higher severity of symptoms in Long COVID patients.

### **2. Study Objectives**

#### **2.1. Primary**

- To provide an overview of the symptoms and characteristics of Long COVID patients at [name] General Hospital.
- To determine whether vaccination against SARS-CoV-2 could improve clinical outcomes and quality of life of Long COVID patients at [name] General Hospital.

#### **2.2. Secondary**

- To determine whether vaccination against SARS-CoV-2 could increase functional exercise capacity of Long COVID patients at [name] General Hospital.
- To determine whether vaccination against SARS-CoV-2 could reduce symptoms, duration, and frequency of Long COVID at [name] General Hospital.

### **3. Study Location**

Patient consent and data collection and analysis will occur at the hospital facility in [name] General Hospital.

#### 4. Study Duration and Timeline

No.	Activity	Description	Timeline
1.	Preparation and approval of the proposal	Create and revise proposals and activity plans according to the discussions of the research team and collaborators	September 2021
2.	Ethics approval	Submit an ethical review to the health research ethics committee of FKUI-RSCM	October 2021
3.	Data collection phase I	Collecting data from the patient's medical record	November 2021 – December 2021
4.	Data collection phase II	Collecting data from the online questionnaire, 6MWT, and follow-up	March 2022 – November 2022
5.	Data analysis	Data tidying, completing, and analysis	December 2022 – February 2023
6.	Report writing	Writing the final report on the results of the research	March 2023
7.	Publication	Publication of research results	April 2023

#### 5. Methods

##### 5.1. Study Design

This is a prospective cohort, cross-sectional study involving two hundred and fifty (250) subjects of post-acute COVID-19 patients, receiving outpatient/inpatient care from [name] General Hospital during the acute phase of the infection, any time prior to enrollment in this study.

## 5.2. Study Population and Selection Criteria

All participants will be required to sign a written informed consent, be willing and able to comply with all study requirements, and should meet the following criteria:

1. Adult patients, aged  $\geq 18$  years old with a history of laboratory-confirmed SARS-CoV-2 infection via a positive molecular (RT-PCR) or antigen (lateral flow assay) test, receiving outpatient/inpatient care from [name] General Hospital, any time prior to enrollment in this study
2. Patients with/without comorbidities
3. Willing to fill-out online Long COVID symptoms follow-up questionnaire
4. Willing and able to comply with trial protocol (re-visits and physical testing)

Subjects will be **excluded** from the study based on the following criteria:

1. Patients with no registered medical record number (MRN) at [name] General Hospital
2. Refusal to participate in the study or to sign the informed consent form
3. Any contraindications for 6 Minute Walking Test according to the guidelines of the American Thoracic Society (ATS)
4. Patients with no access to a smartphone or computer (desktop, laptop, or tablet) to fill out the online screening questionnaire
5. Patients who died during or before enrollment in the study

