## 5.3. Recruitment Methods

All patients, aged  $\geq 18$  years old with a history of laboratory-confirmed SARS-CoV-2 infection via a positive molecular (RT-PCR) or antigen (lateral flow assay) test, receiving outpatient/inpatient care from [name] General Hospital (any time prior to enrolment in this study) are offered to be a participant in this study. One of the research team, dr. [name] will be examining the supervision of the primary investigator, dr. [name], DIC, Ph.D., SpPD, and study coordinator, dr. [name], SpPD.

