#### Descriptive study: Cross-sectional sampling

$$n = \frac{Z_{\alpha}^2 P(1 - P)}{d^2} = \frac{1.96^2 \cdot 0.4(1 - 0.4)}{0.1^2}$$

$$n = 92,1 \text{ subjects} \rightarrow 93 \text{ subjects}$$

Legends:

N : Number of subjects

$Z_{\alpha}$  : Z value in 95% confidence index = 1.96

P : Long COVID prevalence according to literature = 0.40

d : Standard deviation = 0.10

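### The eligibility criteria drop section 5.1's acute-phase care condition, so patients who attended only because of Long COVID can enter and raise the reported incidence

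*Combined protocol and SAP*

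**What the plan says.** Protocol section 5.1 describes the 250 subjects as post-acute patients "receiving outpatient/inpatient care from [name] General Hospital during the acute phase of the infection, any time prior to enrollment in this study". Inclusion criterion 1 in section 5.2, with the same wording in the synopsis, requires a laboratory-confirmed infection and "receiving outpatient/inpatient care from [name] General Hospital, any time prior to enrollment in this study", with no reference to the acute phase. Section 5.3 also leaves it out: adults with confirmed infection who had care at the hospital ("any time prior to enrolment in this study) are offered to be a participant in this study".

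The only exclusion tied to the hospital is "Patients with no registered medical record number (MRN) at [name] General Hospital".

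On analysis, the synopsis states that "Descriptive statistics will describe the incidence of long COVID in participants and its characteristics", and SAP section 3.2.1 repeats the aim of describing incidence. The SAP's descriptive sample size uses "Long COVID prevalence according to literature = 0.40" and "d : Standard deviation = 0.10"; in that formula d takes the place of the margin of error. The vaccination comparison is an unadjusted chi-square or Fisher test (synopsis; SAP section 3.2.2).

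**The concern.** The protocol gives two source populations, and the wider one sits in the text that staff apply at screening. Someone who had COVID-19 at home or was treated elsewhere, and who came to this hospital months later for persisting symptoms, meets section 5.2 but falls outside section 5.1. That person has a record number, so no exclusion removes them.

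Such patients are in the study because they have the outcome. An incidence among participants can be interpreted only if entry does not depend on that outcome. The problem differs from volunteer bias, because it would arise even if every invited patient agreed to take part. The analysis cannot repair it as planned: section 5.4 does not list place of acute care or reason for attendance among the data items, and neither is used in any analysis.

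Two results are at stake: the reported Long COVID incidence, and the secondary objective on whether vaccination reduces the frequency of Long COVID.

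**Working it through.** **1. The eligibility texts side by side**

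| Place | Confirmed infection | Care at the hospital | Care tied to acute phase |
|---|---|---|---|
| Section 5.1 | implied | yes | yes |
| Synopsis, criterion 1 | yes | yes | no |
| Section 5.2, criterion 1 | yes | yes | no |
| Section 5.3 | yes | yes | no |

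Three places carry the wider rule and one carries the narrower. Nothing says which prevails.

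**2. The SAP's own figures**

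Descriptive size: n = 1.96² × 0.4 × 0.6 / 0.1² = 92.2, rounded up to 93, as stated. Analytic size: the SAP's formula with P1 = 0.653, P2 = 0.453 and its entered Z-beta of 0.80 gives 93.04, in line with the stated 93 per group. The planning values are therefore usable as a baseline.

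**3. Effect on the incidence**

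Assumption (not in the documents): a share f of participants enters only because of Long COVID and all of them have it; the rest follow the SAP's 0.40. The reported proportion is then 0.40(1 − f) + f, and the bias is 0.60f.

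| f | Proportion | Bias |
|---|---|---|
| 0 | 0.40 | 0 |
| 0.05 | 0.43 | 0.03 |
| 0.10 | 0.46 | 0.06 |
| 0.20 | 0.52 | 0.12 |
| 0.30 | 0.58 | 0.18 |

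The bias passes d = 0.10 when f > 0.10 / 0.60 = 16.7%.

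**4. Effect on the Long COVID frequency comparison**

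Further assumption: 0.653 and 0.453 are read as Long COVID proportions, although the SAP does not name the endpoint behind them. Each group's proportion becomes p(1 − f) + f, with its own f.

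| f in 0.653 group | f in 0.453 group | Proportions | Difference |
|---|---|---|---|
| 0 | 0 | 0.653, 0.453 | 0.200 |
| 0.10 | 0.10 | 0.688, 0.508 | 0.180 |
| 0.20 | 0.20 | 0.722, 0.562 | 0.160 |
| 0.20 | 0.10 | 0.722, 0.508 | 0.215 |
| 0.10 | 0.20 | 0.688, 0.562 | 0.125 |
| 0.20 | 0 | 0.722, 0.453 | 0.269 |
| 0 | 0.20 | 0.653, 0.562 | 0.091 |

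Equal shares shrink the difference to 0.20(1 − f). Unequal shares can enlarge it or shrink it.

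**The case against.** **The passages may be meant to agree.** Section 5.1 also says that the care may lie at any time before enrolment, there meaning acute care at any past date. In section 5.2 the mention of care directly follows the confirmed infection and could be read as care for that infection. On this view criterion 1 is only a shortened form of section 5.1. That reading is possible, but the criterion does not say it, and screening staff would be entitled to apply the wider one. The objection does show that the harm is a possibility, and that nothing establishes how many such patients would come in.

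**Dilution of the vaccine effect.** A reader might infer that these patients must shrink the difference between vaccination groups and cost the study power. The documents do not support this, for three reasons.

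- Shrinkage follows only if f is equal across groups, and no document gives any f.
- Equal f is not the natural assumption. If people enter because they have Long COVID, the group with more Long COVID supplies more of them. Over-sampling cases by the same odds factor of 1.5 in both groups gives 0.738 and 0.554, a difference of 0.184 with the odds ratio unchanged at 2.27. Power at 93 per group is then about 75%, against 63% under equal f = 0.20 and 79% with no such entry. The size of any loss comes largely from the assumption chosen.
- The primary vaccine objective concerns clinical outcomes and quality of life among Long COVID patients. Adding cases does not dilute that comparison in this way. Only the secondary objective on frequency contrasts cases with non-cases.

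**Later attenders may be in scope for part of the study.** The first primary objective is to describe the symptoms and characteristics of Long COVID patients at this hospital, and later attenders arguably belong there. This stands, and it limits how widely they should be excluded.

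**Conclusion.** The inconsistency is in the text, and the rule that would be applied at screening permits entry on the outcome. The direction of the bias in the reported incidence is upward. Its size cannot be fixed from the documents: 0.06 to 0.18 for f between 0.10 and 0.30, on the assumption that all such entrants have Long COVID and everyone else follows the 0.40.

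For the secondary frequency comparison the claim is only that it can be distorted either way. With f at 20% in one group and 0% in the other, the planned 0.20 difference becomes about 0.09 or 0.27, if the SAP's two proportions are Long COVID proportions. The figures do not justify a statement about lost power, or that the primary quality-of-life comparison is diluted. The passages should be reconciled before the incidence is interpreted.

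**What to change.** Bring criterion 1 (synopsis and section 5.2) and section 5.3 into line with section 5.1 by requiring outpatient or inpatient care at the hospital for the confirmed infection during its acute phase. Check it at enrolment from the medical record and from the infection history that section 5.4 already collects. The phase I record extract is not enough: under section 4 it ends in December 2021, while questionnaires and visits run from March to November 2022, so it misses later infections.

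If later attenders are to be kept:

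- record route of entry for every participant;
- exclude them from the incidence estimate and from the comparison of Long COVID frequency by vaccination status;
- let them stay in the description of Long COVID patients;
- report the quality-of-life comparison among Long COVID patients with and without them.

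The cost is one clause in three places, a record check at enrolment, and a somewhat smaller eligible pool. No stated sample size changes. The fix does not stop symptomatic patients from volunteering more readily than others, and the report should say so.
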